- To characterize the relationship between serum concentration of the active leflunomide metabolite, teriflunomide (A77 1726), and toxicity.
- To assess the relationship between serum concentration of the active leflunomide metabolite, teriflunomide A77 1726), and disease response.

Exploratory Ex-Vivo and Molecular Objectives (Phase I and II)

- To explore the relationship between polymorphisms in the *CYP1A2*, *CYP2C19*, or *DHODH* genes and toxicity/response. *CYP1A2*, *CYP2C19* are the hepatic enzymes responsible for leflunomide metabolism.
- To explore the *ex vivo* cytotoxicity of leflunomide toward primary MM cells, in order to evaluate whether individual *ex vivo* leflunomide response might be a useful predictor of therapeutic response.
- To explore the potential additive or synergistic effects of combining leflunomide with other classes of FDA-approved drugs. The classes include HDAC inhibitors, immunomodulatory drugs [IMiDs], proteasome inhibitors, steroid hormones, and antibody therapeutics such as the CD38 antibody daratumumab.
- To generate a preliminary RNA/miRNA and DNA-methylation signature associated with response of MM cells to leflunomide *in vivo* and teriflunomide *ex vivo*.

Study Design:

This study will be conducted as a single center, single agent phase I/II trial.

The phase I portion will implement a modified rolling six dose escalation design, a more conservative version of the rolling six design of Skolnik, et al. [1], for enrollment with dose escalation, de-escalation, or expansion of a cohort on the basis of the occurrence of dose limiting toxicities (DLTs) during cycle 1.

The starting dose of leflunomide is 20mg daily, with the intention to test up to 60mg daily. Escalation will proceed in increments of 20mg/day (odd numbered dose levels); de-escalation will proceed in decrements of 10mg/day. Up to six doses of leflunomide will be considered:

Dose Level	Leflunomide Dose*
-1	10 mg PO daily
1	20 mg PO daily
2	30 mg PO daily
3	40 mg PO daily
4	50 mg PO daily
5	60 mg PO daily

*NOTE: Leflunomide is administered with a loading dose of 100 mg for the 1st three doses.

The highest dose level that produces $\leq 1/6$ DLTs in cycle 1 will be the MTD. The RP2D of leflunomide will generally be the MTD, but it may be less than the MTD based on a review of available data/cumulative toxicities.

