
Leflunomide will be administered orally at an initial dose of 20 mg daily following a loading dose of 100 mg per day for the first three days of administration. For the phase I portion of the study, five daily dose levels of leflunomide may be tested (10, 20, 30, 40 or 60 mg daily) There will be no intra-patient dose escalation. The R2PD will be used as the daily dose for the phase II portion of the study. At the end of the study, all participants will receive 11 days of oral cholestyramine treatment (8 g three times daily) to reduce the plasma leflunomide levels.

Clinical Observations and Tests to be Performed:
 
Clinical observations will include tolerance as well as response to treatment. Baseline studies will include: history and physical, pulmonary function test, skeletal survey and bone marrow aspiration and biopsy (the bone marrow aspiration will be used for clinical assessment and leftover samples will be used for correlative laboratory studies), as well as a laboratory evaluation to include CBC with differential, comprehensive chemistry panel (to include LDH, magnesium, phosphorus and uric acid) and myeloma labs (serum protein electrophoresis, serum immunofixation, 24-hour urine protein electrophoresis, urine immunofixation, serum free light chains, and quantitative immunoglobulins). Clinical observation of response will take place on day 1 of each 28-day cycle. Subjects will be evaluated through clinic visits and physical exams as well as laboratory tests to include CBC with differential, comprehensive chemistry panel and myeloma labs. Blood tests will be performed at a minimum of every 28 days but may be done more frequently as clinically indicated. A skeletal survey may be repeated as clinically indicated. Patients will undergo toxicity assessment every two weeks for the first three cycles following initiation with leflunomide and will undergo, at a minimum, monthly toxicity assessments thereafter. For all phase II patients and phase I patients enrolled at the anticipated RP2D, a second bone marrow aspiration will be conducted for correlative laboratory studies on day 1 of cycle 2. Confirmation of complete response (CR), stringent complete response (sCR), and progressive disease (PD) will involve bone marrow aspiration and, for patients who have enrolled in the phase II portion, leftover samples from these bone marrow aspirations will be used

for correlative laboratory studies.
Statistical Considerations:

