5.3 Phase I/II Treatment Plan

This phase I trial will implement a modified rolling six dose escalation, de-escalation, expansion design, a more conservative version of the rolling six design of Skolnik, et al. [1] to ensure safety and to allow for the evaluation of toxicities associated with leflunomide. See [Section 13.3.2](#) for dose escalation/de-escalation/expansion rules, and Section [13.1](#) for the definition of dose limiting toxicity (DLT).

Up to six doses of leflunomide will be considered (see Table 5.3.1). The starting dose of leflunomide is 20mg daily, with the intention to test up to 60mg daily. Escalation will proceed in increments of 20mg/day (odd numbered dose levels); de-escalation will proceed in decrements of 10mg/day. There will be no intra-patient dose escalation; participants will undergo dose modification due to toxicity per [Section 6.2](#).

Table 5.3.1: Dose Levels

Dose Level	Leflunomide Dose*
-1	10 mg PO daily
1	20 mg PO daily
2	30 mg PO daily
3	40 mg PO daily
4	50 mg PO daily
5	60 mg PO daily

*NOTE: Leflunomide is administered with a loading dose of 100 mg for the 1st three doses.

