5.5 Agents Administration

5.5.1 Leflunomide

Participants will be instructed to take each dose of leflunomide orally, once a day, at approximately the same time each day. They may take it with or without food. If a patient forgets or misses a dose for whatever reason, it should **not** be replaced or made up. Participants will be given a study calendar (pill diary) to document each dose of leflunomide that is taken or missed.

NOTE: On study visit days, participants should refrain from taking leflunomide until after blood is collected.

Leflunomide is administered with a loading dose of 100 mg per day for the first three doses (first three days).

There will be no intra-patient dose escalation; patients will undergo dose modification due to toxicity per [Section 6.2](#).

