8.1.7 Agent administration

Leflunomide is administered orally. Participants will be given a study calendar to track all doses taken or missed. There will be an initial loading dose of 100 mg per day for the first 3 days of doses. Participants will then receive leflunomide at the assigned dose level. See [Section 5.5.1](#) for administration details.

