10.0 STUDY CALENDAR

Table 10 describes required procedures. All procedures may increase in frequency if clinically indicated or oriented following toxicity. Adjustments to the treatment cycle due to a hold in study agent are detailed in [Section 5.2](#).

Table 10.0 Study Activity Calendar

	Screening ^a	Cycle 1, 2, 3		Cycle 4+ ^d	End of Treatment ^e				Active Follow-Up ^j	Long Term Follow-Up ^k
		Day 1 ^b	Day 14 ^c		Day 0 ^f	Days 1-11 ^g	Day 14 ^h	Day 30 ⁱ		
Informed Consent ^l	X ^u									
Inclusion/Exclusion Criteria ^m	X									
Registration ⁿ	X ⁿ									
Medical history ^o	X									
Physical exam	X	X		X					X	
Vital signs ^p	X	X		X					X	
Adverse events assessment ^q		X	X	X	X	X			X	
Concomitant meds review	X	X		X	X				X	
ECOG status ^r	X	X		X					X	
Pregnancy test ^s	X									
TB antigen test ^t	X									
Hepatitis A, B, C testing	X ^u									
Pulmonary function test	X ^u									
Extramedullary disease survey ^v	X ^u			X ^w	X ^w				X ^w	X ^w
Skeletal survey	X ^u									
Clinical bone marrow aspiration/biopsy with research use of leftover samples	X ^{u,y}	X ^{y,z,aa}		X ^{y,z}	X ^{y,z}				X ^{y,z}	X ^{y,z}
Research bone marrow aspiration		X ^{bb}								
CBC with differential ^{cc}	X	X	X	X					X	X
Chemistry panel ^{dd}	X	X	X	X					X	X
Myeloma labs ^{ee}	X	X ^{kk}		X	X				X	X
Response assessment ^{ff}		X ^{aa}		X	X				X	X
Research blood samples ^{gg}		X	X	X	X					
Teriflunomide clinical testing ^{hh}				X		X ⁱⁱ	X ⁱⁱ			
Leflunomide administration ^{jj}		Daily								
Cholestyramine ^g					X ^g					
Survival										X ^k

a. All screening procedures to be performed within 21 days of start of study agent except informed consent, acute hepatitis panel, skeletal survey, bone marrow biopsy, and pulmonary lung function test which may occur within 30 days of start of treatment (footnote u) and except for registration which must occur within 7 days from start of treatment (footnote n).

- b. Day 1 assessments to be performed within 5 days (120 hours) prior to Day 1 drug (except footnote u for C1 only). Day 1 safety assessments must be resulted and reviewed prior to administration of agent for the cycle that is initiating. Screening assessments, if performed within this aforementioned time frame, may serve as C1D1 assessments. Note: items with footnote "aa" are not performed for C1D1; the windows for screening assessments still apply.
- c. Day 14 evaluations have +/- 3 day window.

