- ff. See [Section 11.1](#) for response assessment criteria.
- gg. Research blood sample collection will occur at the time of blood collection for clinical labs. Venous blood will be collected into three 4-mL purple top (EDTA) tubes, gently agitated, placed on ice and brought promptly (so that the sample can be processed within the hour) to the APCF in Shapiro room 1042. Notify the APCF ([name] or her representative) by e-mail to [contact] in advance of sampling (ideally at least a day in advance). Discarded cells from one sample will contribute to pharmacogenomic studies ([Section 9.3.1](#)). Changes in laboratory contact information will not be considered protocol deviations.
- hh. Teriflunomide clinical blood assay to be ordered as "leflunomide metabolite" miscellaneous clinical test.
- ii. Clinical testing must demonstrate teriflunomide plasma levels less than 0.02 mg/L or 0.02 µg/ml by two separate tests at least 14 days apart. If plasma levels are higher than 0.02 mg/L or 0.02 µg/ml, additional cholestyramine treatment will be considered.

jj. Participants will receive leflunomide orally on a daily basis which will be recorded on the pill diary. The first 3 loading doses will be given at a dose of 100 mg, after which treatment will continue at a dose of 20 or 10 mg daily. See administration details in [Section 5.5.1](#). **NOTE: On study visit days, participants should refrain from taking leflunomide until after blood is collected.**

kk. Myeloma labs may be repeated at C1D1 per investigators discretion and used for disease response assessment

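### Two dose statements contradict the rest of the protocol: calendar footnote jj gives only 20 or 10 mg daily after loading, and the synopsis dosage paragraph omits the 50 mg level

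*Combined protocol and SAP*

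**What the plan says.** **Footnote jj.** Section 10.0 introduces the calendar with the words "Table 10 describes required procedures". The leflunomide row carries footnote jj, which gives the three 100 mg loading doses and then says "after which treatment will continue at a dose of 20 or 10 mg daily". It sends the reader to Section 5.5.1 for details. That section states "Leflunomide is administered with a loading dose of 100 mg per day for the first three doses (first three days") and names no maintenance dose.

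**Dose levels elsewhere.** The Study Design part of the synopsis says "Up to six doses of leflunomide will be considered" and tabulates 10, 20, 30, 40, 50 and 60 mg. Tables 5.3.1 and 13.3.1 list the same six. Section 8.1.7 says of the period after loading: "Participants will then receive leflunomide at the assigned dose level". Section 13.4 builds the phase I sample size on patients at 20, 40 and 60 mg.

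**Synopsis dosage paragraph.** Under Investigational Product Dosage and Administration, the synopsis says "five daily dose levels of leflunomide may be tested (10, 20, 30, 40 or 60 mg daily"). The same paragraph says of phase II: "The R2PD will be used as the daily dose for the phase II portion of the study".

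**The concern.** In a dose-escalation trial the assigned daily dose is the quantity under study. Footnote jj sits where site staff look up what happens at each visit. Read literally, it gives anyone assigned above 20 mg a daily dose other than the assigned one. This applies to the phase I cohorts and, if the RP2D is above 20 mg, to phase II. Dose-limiting toxicities would then be credited to a level that the patient did not take.

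The synopsis paragraph raises a related problem. A level absent from its list is present in the tables, where it is available for de-escalation from 60 mg and so is a possible MTD. The dose reductions in Table 6.2.2 also step down through lower doses, so they too depend on an agreed list. Section 7.1 notes that the trial goes above the approved dose, which makes consistent dose text more important.

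**Working it through.** **1. The plan's own figures.** Section 13.4 gives a maximum of 36 participants at 6 per level.

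- Six levels: 6 × 6 = 36, which reproduces the stated figure.
- Five levels, as in the synopsis dosage paragraph: 5 × 6 = 30, which does not.

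Section 13.4's well-tolerated path is 3 (20 mg) + 3 (40 mg) + 6 (60 mg) = 12, as stated. With 6 replacements it is 18, also as stated.

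**2. The dose statements side by side.**

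| Place | Daily dose after loading |
|---|---|
| Synopsis, Study Design table | 10, 20, 30, 40, 50, 60 mg |
| Table 5.3.1 | 10, 20, 30, 40, 50, 60 mg |
| Table 13.3.1 | 10, 20, 30, 40, 50, 60 mg |
| Section 8.1.7 | the assigned level |
| Section 13.4 | planned cohorts at 20, 40, 60 mg |
| Synopsis, dosage paragraph | 10, 20, 30, 40, 60 mg |
| Table 10, footnote jj | 20 or 10 mg |

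Footnote jj covers 2 of the 6 tabulated levels and omits 30, 40, 50 and 60 mg. The dosage paragraph covers 5 of 6 and omits 50 mg.

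**3. Can the omission of 50 mg be deliberate?** Escalation moves by 20 mg/day from 20 mg (20, 40, 60), and de-escalation by 10 mg/day. The first step down from 60 mg is 60 − 10 = 50 mg, so the level is reachable. The 30 mg level is also reached only by stepping down (40 − 10 = 30), yet the dosage paragraph lists it. A rule of naming only escalation levels therefore does not explain the gap.

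**4. How many planned patients fall outside footnote jj?** This uses assigned doses, before any toxicity reduction.

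- Section 13.4 path, no replacements: 3 + 6 = 9 of 12 = 75%.
- With 6 replacements, all at 20 mg: 9 of 18 = 50%.
- With 6 replacements, all at 40 or 60 mg: (9 + 6) of 18 = 15 of 18 = 83%.
- If 6 patients are treated at each of 20, 40 and 60 mg, which Section 13.3.2 allows: 12 of 18 = 67%.

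**5. A conditional illustration.** Section 13.2 ties evaluability for dose escalation to receiving at least 75% of leflunomide in cycle 1. Assume that this is counted in mg, with a 28-day cycle, 3 loading days, 25 maintenance days and no missed doses. A patient given 20 mg under footnote jj receives 3 × 100 + 25 × 20 = 800 mg.

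- Assigned 40 mg: 300 + 25 × 40 = 1,300 mg; 800/1,300 = 62%.
- Assigned 60 mg: 300 + 25 × 60 = 1,800 mg; 800/1,800 = 44%.

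Both are below 75%, so such a patient would not count as evaluable unless a DLT occurred. If the 75% were counted in doses taken instead, the same patient would stand at 28/28 = 100% and the discrepancy would not show.

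**The case against.** The strongest reply concerns weight. The dose a patient receives is controlled elsewhere:

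- Under Section 4.3 the Data Coordinating Center assigns the level and emails a confirmation, with the level, to the study team including the investigational pharmacy.
- Section 8.1.7 refers to the assigned level.
- Section 7.3 keeps a log of levels administered.
- Section 12.2.3 sends ambiguities to the principal investigator.

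The synopsis dosage paragraph says only that levels may be tested, while the escalation rules and tables in Sections 5.3 and 13.3 agree with one another. The percentages rest on illustrative paths.

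Much of this stands. The safeguards lower the risk of a dosing error, and the percentages measure mismatched text only. The synopsis omission is the lesser half and alone would be close to editorial. What does not stand is the inference that nothing needs correcting. Footnote jj has no wording that confines it to a dose level or to reductions, and its cross-reference leads to a section with no maintenance dose. Taking its figures as tablet strengths fails because the sentence calls them a dose. The safeguards work around the conflict and leave it in the protocol.

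**Conclusion.** Both contradictions are present in the current text, and they should be fixed. Footnote jj is the more serious: it sits on the calendar's dosing row and agrees with 2 of 6 levels, leaving 9 of 12 patients on the planned path (50% to 83% with all six replacements) with an assigned dose it does not list. Those counts assume no DLTs on that path. The synopsis dosage paragraph omits one of six levels and does not fit the stated maximum of 36. No endpoint, planned sample size or duration figure is affected, and no estimate of dosing errors is made. The documents do not settle which statement reflects the intended dosing, and this review does not choose between them.

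**What to change.** Reconcile footnote jj of Table 10 and the synopsis dosage paragraph with the synopsis dose table, Tables 5.3.1 and 13.3.1, Section 8.1.7 and Section 13.4, so that all give one set of dose levels. The sponsor decides which doses apply. Section 5.5.1 should be checked in the same pass, since footnote jj relies on it.

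If the six-level tables stand, the cost is a wording amendment in two places, with no extra patients and no change to endpoints, analysis, sample size or duration. If another set is intended, the three tables and the count in Section 13.4 must be revised to match.

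As an optional clarification, Table 13.3.2 could state how its move to the next higher level relates to the odd-numbered-level escalation rule given elsewhere in the protocol.

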11.0 EVALUATION CRITERIA/MEASUREMENT OF EFFECT

11.1 Phase I/Primary Endpoint: Toxicity

The primary endpoint is toxicity. Toxicity will be graded according to the NCI-Common Terminology Criteria for Adverse Events version 4.03. Dose limiting toxicity (DLT) is defined in [section 13.1](#) of the protocol. The MTD will be based on the assessment of DLT during cycle 1. All patients who are not evaluable for dose limiting toxicity will be replaced.

11.2 Phase II/Primary Endpoint: Response

The primary endpoint is response. Response will be categorized using the IMWG response criteria for multiple myeloma [37, 38]. Table 11.2 summarizes the categories and criteria.

Table 11.2 Response Criteria

Response Category	Response Criteria
Complete response (CR)*	Negative immunofixation of serum & urine, AND Disappearance of any soft tissue plasmacytomas, AND < 5% plasma cells in bone marrow
Stringent complete response (sCR)*	CR (as defined above) PLUS: Normal FLC ratio, AND Absence of clonal cells in bone marrow by immunohistochemistry or immunofluorescence
Very good partial response (VGPR)**	Serum and urine M-component detectable by immunofixation but not on electrophoresis, OR ≥ 90% reduction in serum M-component plus urine M-component < 100mg per 24h
Partial response (PR)**	≥ 50% reduction of serum M protein and reduction in 24h urinary M protein by ≥ 90% or to < 200mg per 24h If serum and urine M protein are unmeasurable, a ≥ 50% decrease in the difference between involved and unininvolved FLC levels is required in place of the M protein response criteria If serum and urine M protein are unmeasurable, AND serum free light assay is also unmeasurable, a ≥ 50% reduction in bone marrow plasma cells is required in place of M protein, provided baseline percentage was ≥ 30%. In addition to the above criteria, if present at baseline, ≥ 50% reduction in the size of soft tissue plasmacytomas is also required
Minimal Response	• 25% but ≤ 49% reduction of serum M protein and reduction in 24-hour urine M-protein by 50 to 89% which still exceeds 200 mg per 24 hr

Response Category	Response Criteria
(MR)**, ***	
 In addition to the above criteria, if present at baseline, 25-49% reduction in the size of soft tissue plasmacytomas is also required No increase in size or number of lytic bone lesions (development of compression fracture does not exclude response)
Stable disease (SD)**	Not meeting criteria for CR, VGPR, PR, or PD
Progressive disease (PD)**	
Increase of 25% from lowest response value in any one or more of the following:
 
 Serum M-component (absolute increase must be ≥ 0.5 g/100ml), and/or Urine M-component (absolute increase must be ≥ 200mg per 24h), and/or Only in patients without measurable serum and urine M-protein levels: 
 The difference between involved and unininvolved FLC levels (absolute increase must be > 10mg/dl) Bone marrow plasma cell percentage (absolute % must be $\geq 10\%$) Definite development of new bone lesions or soft tissue plasmacytomas OR definite increase in the size of existing bone lesions or soft tissue plasmacytomas Development of hypercalcemia (corrected serum calcium > 11.5mg/100ml) that can be attributed solely to the plasma cell proliferative disorder

* Confirmation with bone marrow assessment is required for CR and sCR. Only a single bone marrow assessment is needed. CR and sCR require no known evidence of progressive or new bone lesions if radiographic studies are performed.

** The following response categories: VGPR, PR, MR, SD, and PD require 2 consecutive assessments made at any time before the institution of any new therapy. VGPR, PR, MR, and SD require no known evidence of progressive or new bone lesions if radiographic studies are performed. The second assessment might be at the time of a planned assessment or earlier, based on the judgement of the treating physician.

*** Based on the recommendations in Rajkumar et al. [38], MR will be reported separately and will be distinguished from PR or better.

11.3 Phase II/Secondary Endpoints:

Best Overall Response:

Based on the International Myeloma Working Group (IMWG) criteria, best overall response is the best response (sCR/CR/VGPR or PR) recorded from the start of treatment until disease progression. Confirmation of sCR/CR/VGPR or PR assessed by IMWG criteria.

Response Duration:

Defined as the time interval from the date of first documented response (sCR/CR/VGPR or PR) to documented disease progression or death whichever occurs first.

Clinical Benefit Response:

Based on the International Myeloma Working Group (IMWG) criteria, clinical benefit response is the best response (sCR/CR/VGPR/PR/MR or SD) recorded from start of treatment until disease progression. Confirmation of sCR/CR/VGPR/PR/MR or SD assessed by IMWG criteria.

Overall Survival:

Defined as the time interval from date of first dose of study drug to date of death from any cause.

Progression-Free Survival:

Defined as the time interval from date of first dose of study drug to first documented disease progression or death from any cause, whichever occurs first.

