3.0 PATIENT ELIGIBILITY

3.1 Inclusion Criteria

Participants must meet the following criteria on screening examination to be eligible to participate in the study:

Patient MRN:	Patient Initials (F, M, L):
--------------	-----------------------------

Informed Consent

1. All subjects must have the ability to understand and the willingness to sign a written informed consent.

Age Criteria, Performance Status, and Life Expectancy

2. Patients must be age \geq 18 years.

3. Patients must have a life expectancy of > 3 months.

4. Patients must exhibit an ECOG performance status of 0-2.

Nature of Illness and Treatment History

5. Patients must have a diagnosis of multiple myeloma.

6. Patients must have measurable disease, defined as one of the following within 21 days prior to registration:

- Serum M-protein ≥ 0.5 g/dL
- Urine M-protein ≥ 200 mg/24 hr
- Serum free light chain ≥ 10 mg/dL provided the FLC ratio is abnormal.
- 10% plasma cells in bone marrow

7. Patients must be relapsed or are refractory to at least 3 prior lines of therapy, including both a proteasome inhibitor and an IMiD, and for whom transplant is not recommended (induction therapy and stem cell transplant +/- maintenance will be considered as one regimen).

8. At least 2 weeks from prior therapy to time of start of treatment. Prior therapy includes steroids (except prednisone or equivalent – up to 10 mg per day is allowed).

Clinical laboratory parameters

9. Platelet count $\geq 50,000/\mu\text{L}$. Platelet transfusions are not allowed within 14 days of platelet assessment.

10. ANC $\geq 1000/\text{mm}^3$. Growth factor is not permitted within 14 days of neutrophil assessment.

11. AST and ALT $< 2.0 \times \text{ULN}$.

12. Total Bilirubin $< 1.5 \times \text{ULN}$.

13. Calculated creatinine clearance (CrCl) ≥ 30 mL/min per 24-hour urine collection or the Cockcroft-Gault formula.

$$\text{CrCl (mL/min)} = \frac{(140-\text{age}) \times \text{actual body weight (kg)}}{72 \times \text{serum creatinine (mg/dL)}} \quad (\times 0.85 \text{ for females})$$

Or

$$\text{CrCl (mL/min)} = \frac{(140-\text{age}) \times \text{actual body weight (kg)}}{0.8136 \times \text{serum creatinine (umol/L)}} \quad (\times 0.85 \text{ for females})$$

- 14. Negative serum or urine β -HCG test (female patient of childbearing potential* only), to be performed locally within the screening period.
- 15. Negative for tuberculosis antigen (e.g. T-Spot test).
- 16. Negative for hepatitis A, B, or C infection.

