⁺: Although under this scenario escalating to the next higher dose level is suggested, additional patients can be accrued to the current level -up to n=6 patients.
^{**}: Patients treated on a higher dose will have their treatment modified to the dose below the dose level with 2 DLTs, if pending patients have DLT.

Phase II Design

Following completion of the phase I portion of the study and identification of the RP2D, the phase II portion of the study will be initiated. Recent studies evaluating daratumumab, a CD38 monoclonal antibody, as monotherapy for relapsed/refractory multiple myeloma were recently published [39, 40] and have led to FDA approval of this agent. One study included patients with relapsed multiple myeloma treated with at least three lines of therapy while the other included patients treated with at least two prior lines of treatment. Treatment with daratumumab as a single agent lead to an overall response rate of 29.2% and 36% respectively in each of these studies. In both studies, the agent investigated was well tolerated but required IV dosing once weekly for 8 doses, followed by twice-monthly doses for 8 doses and then monthly thereafter. We suspect leflunomide to be similarly well tolerated but with a more convenient dosing schedule. Because we are including patients who have received at least three prior lines of treatment, we will target an overall response rate of 30% for the phase II portion of the study.

This single-center, single arm phase II trial will implement a Simon Two-Stage Optimal Design [2, 3]. to evaluate the anti-myeloma activity of leflunomide, when given as a single agent, as assessed by overall response rate (ORR), in patients with relapsed or relapsed/refractory MM. The phase II portion of the study is expected to enroll a minimum of 19 and a maximum of 39 patients. The sample size is based on the desire to discriminate a promising ORR of 30% from a disappointing response rate of 15% using a type I error rate of 0.10 and power of 80%.

At stage 1, 19 patients will be entered on the study. If ≤ 3 responses are seen, the study will be terminated. If at least 4 patients achieve response, the trial will continue to the second stage. The 6 patients treated at the RP2D in the phase I portion will be evaluated as part of this phase II group. The probability of early stopping after the first stage is 0.68.

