At stage 2, 20 additional patients will be entered. At the end of stage 2, if 9 or more patients respond, leflunomide -as single agent therapy, will be considered worthy of further study. If ≤ 8 patients respond further investigation is not warranted.

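### Table 11.2 lets some patients who enter on free light chains alone or marrow alone meet VGPR or CR before the first dose, and nothing stops them counting in ORR

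*Combined protocol and SAP*

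**What the plan says.** Section 3.1, criterion 6, asks for any one of four markers. Two of them are not M-protein: "Serum free light chain ≥ 10 mg/dL provided the FLC ratio is abnormal", and 10% plasma cells in the marrow.

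Table 11.2 (section 11.2) then defines response:

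- **CR** begins "Negative immunofixation of serum & urine, AND" and adds disappearance of plasmacytomas and fewer than 5% marrow plasma cells. It has no FLC term; a normal FLC ratio appears only under sCR.
- **VGPR** has two routes. The first is "Serum and urine M-component detectable by immunofixation but not on electrophoresis". The second is a fall of at least 90% in serum M-component with urine below 100 mg per 24 h.
- **PR** provides for patients without measurable M-protein: a fall of at least 50% in the FLC difference or, if FLC is also unmeasurable, a fall of at least 50% in marrow plasma cells, provided the baseline was 30% or more. It ends: "In addition to the above criteria, if present at baseline, ≥ 50% reduction in the size of soft tissue plasmacytomas is also required".
- **SD** is whatever is not CR, VGPR, PR or PD.

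The footnotes confirm VGPR by two consecutive assessments and CR by a single marrow assessment. Sections 11.3 and 13.5 take best response from the start of treatment and count confirmed PR or better as ORR. The phase II rule in section 13.3 is: "At stage 1, 19 patients will be entered on the study. If ≤ 3 responses are seen, the study will be terminated". Then "At stage 2, 20 additional patients will be entered", and 9 or more responders in 39 make the drug worthy of further study.

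**The concern.** For patients with no M-protein on electrophoresis, the deeper category asks for less than PR. PR needs a measured fall in the patient's own marker. The first VGPR route needs only an immunofixation and electrophoresis pattern that the patient may have brought to screening, and CR can be met with the FLC still abnormal. A patient whose disease does not move could then be scored as a responder in the primary endpoint. SD cannot take such a patient, because SD is defined by not meeting the higher categories.

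The two-stage rule has thin margins (4 of 19, then 9 of 39), so even one or two such patients would matter to the decision. Their response duration would also start at the first assessment.

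**Working it through.** **1. Who can meet a responder row at screening?**

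| Entry marker | VGPR, first route | CR |
|---|---|---|
| Serum or urine M-protein | No: must lose the electrophoresis signal | No: must become immunofixation-negative |
| FLC only | Yes, if serum and urine are immunofixation-positive and electrophoresis-negative | Yes, if immunofixation-negative, marrow below 5%, no plasmacytoma |
| Marrow only (10% or more) | Yes, same pattern | No: CR needs below 5% |

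sCR cannot be met at screening by an FLC-entry patient, because it needs a normal ratio. The second VGPR route is a change from baseline and is not at issue. I found no statement in sections 11.2, 11.3, 13.2 or 13.5 that a category already met at baseline is not a response.

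**2. The plan's own figures.** Inputs from section 13.3: null rate 0.15, target 0.30, continue if at least 4 of 19, succeed if at least 9 of 39. Write b(x; n, p) for the binomial probability.

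- Early stopping at 0.15: sum of b(x; 19, 0.15) for x = 0 to 3 = 0.684 (stated 0.68).
- False-positive rate: sum over x = 4 to 19 of b(x; 19, 0.15) × P(Bin(20, 0.15) ≥ 9 − x) = 0.097 (stated 0.10).
- Power, same sum at 0.30: 0.803 (stated 80%).

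The design reproduces, and a grid search returns it as the Simon optimal design. The sample size is not in question.

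**3. One patient who qualifies at baseline, all others responding at 15%.**

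- In stage 1: the other 18 must give at most 2 responses to stop. P(Bin(18, 0.15) ≤ 2) = 0.480, and P(declare worthy) = 0.180.
- In stage 2: early stopping stays at 0.684, and P(declare worthy) = 0.151.
- Placed at random among 39: (19/39) × 0.180 + (20/39) × 0.151 = 0.165. Early stopping is (19/39) × 0.480 + (20/39) × 0.684 = 0.585.

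Two such patients placed at random give 0.261, with early stopping 0.480.

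**4. As a share of the population.** If a share f qualifies at baseline, the counted rate is f + (1 − f) × 0.15 = 0.15 + 0.85f.

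| f (assumed) | Counted rate | Early stopping | P(declare worthy) |
|---|---|---|---|
| 0 | 0.150 | 0.684 | 0.097 |
| 2.5% | 0.171 | 0.586 | 0.176 |
| 5% | 0.193 | 0.488 | 0.278 |
| 10% | 0.235 | 0.315 | 0.511 |

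The documents give no value for f. The last row would need about 4 of 39 patients with a narrow profile.

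**The case against.** The best reply is that section 11.2 makes the IMWG criteria govern and calls Table 11.2 a summary of them. The cited papers may close the gap. That cannot be checked from the documents, and it limits the claim to what the table says. It does not remove the point: the table is the only definition given, and because its PR row spells out the FLC and marrow substitutes, their absence from VGPR and CR can be read as intended.

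The profiles are also narrow, and the schedule makes some of them harder to score. Read literally, the first VGPR route needs both serum and urine to show the pattern. Study calendar footnote ee schedules 24-hour urine after baseline only to confirm CR or in urine-only disease, so for an FLC-only patient the urine half of a confirmed VGPR would rest on the screening result. Footnote z repeats the marrow only when CR, sCR or PD is suspected, so a baseline CR would have to be suspected in an unchanged patient. These points lower the likely number and stand as limits.

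A reader might infer three stronger things, and the documents support none of them. First, that VGPR and CR ask for no improvement from anyone: patients who enter on M-protein must improve, and marrow-entry patients must clear to below 5% for CR. Second, that the missing plasmacytoma term in VGPR is another response without drug effect: a patient who reaches VGPR by a 90% M-component fall with an unchanged plasmacytoma has had a real fall. It is an inconsistency between rows, no more. Third, that the trial's error rate is in fact inflated by a known amount: the number of affected patients is unknown.

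**Conclusion.** The concern holds in a limited form. As Table 11.2 is written, some FLC-only patients meet VGPR or CR at baseline, and some marrow-only patients meet VGPR. Nothing in the documents keeps such unchanged patients out of ORR.

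The size depends on an unknown count. For illustration, a single such patient is enough to take the false-positive rate above the planned 0.10: about 0.165 if placed at random among 39, and 0.18 if in stage 1, where early stopping falls from 0.68 to 0.48. These figures assume a true ORR of 15% in all other patients, that the patient stays in the same state and is scored by the literal table, and that nothing in the cited criteria overrides it. With no such patients the design keeps its planned properties. The wording should be corrected before responses are scored.

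**What to change.** Amend Table 11.2:

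1. State that a VGPR or CR category whose conditions were already met at baseline is not a response.
2. Limit the immunofixation/electrophoresis route to VGPR to patients with M-component detectable on electrophoresis at baseline.
3. For FLC-only patients, require an FLC improvement from baseline for VGPR and a normal FLC ratio for CR.
4. Separately, for consistency between rows, carry the PR row's plasmacytoma requirement into VGPR.

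Do not simply require at least PR in the entry marker. The PR marrow route applies only from a baseline of 30%, while criterion 6 admits from 10%, so marrow-only patients at 10–29% could never respond, even if their marrow cleared. Those two passages must be reconciled first.

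The cost is mainly wording. Serum and urine studies are done at baseline for everyone, and FLC is part of the regular myeloma labs, so items 1 to 3 need no new tests. Sample size and decision rule stay as they are. Any rule that relied on repeat urine or marrow values would need more, because footnotes ee and z do not schedule them routinely and the cycle 2 day 1 marrow is a research sample. The downside is that observed ORR may be slightly lower.
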